## 5.8 Statistical methodology and assumptions

### 5.8.1 Two sample t-test

For Population I, the two-sample t-test will be used in order to obtain 95% confidence intervals for the difference between:

- each continued BYM338 dose arm vs. corresponding placebo, and
- Each continued BYM338 dose arm vs. continued placebo arm,

for the following endpoints:

- Week 25 to 49 on the 6MWT
- Week 25 to 49 on the SPPB
- Week 25 to 49 on the Gait speed
- Week 25 to 49 in log transformed values on LBM and ASMI

The t-test will assume Equal variances when the null hypothesis of variance equality cannot be rejected, and Unequal variances when the variance equality hypothesis is rejected.

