3.1 Study design

This Phase IIb extension study is a 24 weeks off drug follow-up observation trial to determine the durability of effect and the safety of bimagrumab in older patients with sarcopenia.

After completing 24 weeks of treatment in the core study (CBYM338E2202 End of Treatment (EOT) visit), newly consenting patients in the extension study CBYM338E2202E1 will continue with the same uniquely identified patient number that was assigned in the core study and will be followed for an additional 24 weeks off drug (see Figure 3-1). They will complete the end of study (EOS) at week 49.

Patients enrolled prior to this amendment #1, will follow the original study design described below Figure 3-2 and will continue to be treated as per the regimen assigned at entry of the extension study. It is anticipated that approximately a total 45 patients will be followed under this design and 10 to 15 of them will still be in the study at the time of implementing this amendment #1.

Figure 3-1 Study design for patients enrolled after the protocol amendment #1

Exercise program

All patients will be requested to continue their home exercise program (2-3 times each week) as it was prescribed and performed in the core study, CBYM338E2202. At the patient's request, the study staff will be able to provide a new set of exercise instructions in order to encourage study participation and adherence.

The exercise program contains activities for muscle strength, endurance, balance and flexibility, as well as warm-up (i.e. walking) and cool-down periods to improve comfort, prepare the body for increased effort, and reduce the risk of training injuries. The exercise program is described in detail in the CBYM338E2202E1 Outcomes Manual.

Week 25/EOT – Joined Core and Extension visit

All EOT assessments of the core study will be performed 4 weeks after the last dose of study drug as outlined in core study CBYM338E2202. Consenting, eligible patients will start in this extension study on the same day (i.e., EOT visit of CBYM338E2202).

The ability and willingness of the patient to continue performing the home-based exercise program should be re-assessed by the investigator or a team member during this visit.

For a complete list of assessments, please refer to Section 6 [Table 6-1](#).

Subsequent Visits – Weeks 29-45

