5.2 Treatment arms

Patients enrolled following protocol amendment #1 will not receive investigational treatment.

Patients enrolled prior to the protocol amendment #1 have been assigned to one of the following 2 treatment arms in a ratio of 1:1 to receive i.v. doses of the following and will continue with this treatment until their EOT:

1. Patients on BYM338 70 mg in core study were randomized 1:1 to receive either BYM338 70 mg or placebo (BYM 70/PBO) for 6 doses in the extension study
2. Patients on BYM338 210 mg in core study were randomized 1:1 to receive either BYM338 210 mg or placebo (BYM 210/PBO) for 6 doses in the extension study
3. Patients on BYM338 700 mg in core study were randomized 1:1 to receive either BYM338 700 mg or placebo (BYM 700/PBO) for 6 doses in the extension study
4. Patients on BYM338 0 mg (placebo) in core study were randomized 1:1 to receive BYM338 0 mg (placebo) in both arms for 6 doses in the extension study

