9.7 Sample size calculation

All the subjects from the core (CBYM338E2202), if eligible, can enter this extension study after they complete informed consent.

The standard deviation of SPPB can be found in the references in [Table 9-1](#), which are also referred by the core study protocol.

Table 9-1 Standard deviation of SPPB

Reference	Study description	SD
Perera et al (2006)	N=492 community dwelling adults	2.7 (Baseline)
Kwon et al. (2009)	N=424 older sedentary adults	1.42 (Baseline)
Papanicolaou et al (2013)	N=120 sarcopenic elderly women	1.48 (Baseline) 2.19 (After 6 months treatment)

1.93 (After 6 months placebo)

With 40 to 50 patients per each bimagrumab dose arm,, assuming a standard deviation of SPPB of 1.5, 2.0, 2.5, and 3.0, the half-width of 95% confidence interval for SPPB is presented below in [Table 9-2](#).

Table 9-2 Half-width of 95% confidence interval for SPPB

	SD=1.5	SD=2.0	SD=2.5	SD=3.0
50 patients per arm:	0.42	0.55	0.69	0.83
40 patients per arm:	0.46	0.62	0.77	0.93

10 Ethical considerations

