#### **3.5.3.1 6MWT, Gait speed, SPPB total score, total LBM and ASMI**

For population I, the 95% confidence interval will be provided for the difference between each continued BYM dose arm and corresponding placebo (switched from the same BYM dose arm) at each visit. 95% confidence interval will also be provided for the difference between each continued BYM dose arm and the placebo arm continued from the core study at each visit.

The confidence interval at Week 49 for SPPB total score between each continued BYM dose arm and corresponding placebo (switched from the same BYM dose arm) for population I is provided as the primary analysis. For population II, the summary statistics at Week 49 are provided as the primary analysis.

For population II, SPPB total score, 6MWT, Gait speed, total LBM and ASMI at Week 49 will be explored at final analysis using an analysis of variance model (ANCOVA) with treatment assigned in the core study [REDACTED] as fixed effects and Week 25 SPPB total score as covariate.

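### SAP 5.8.1 picks the t interval by a preliminary variance test with little power in Population I's small arms, so the secondary intervals against continued placebo can miss 95% coverage in either direction

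*SAP*

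**What the plan says.** SAP section 5.8.1 states that for Population I "the two-sample t-test will be used in order to obtain 95% confidence intervals for the difference between" two kinds of pair: each continued dose arm against the arm switched from that dose to placebo, and "Each continued BYM338 dose arm vs. continued placebo arm". It lists SPPB, 6MWT, gait speed, and log-transformed LBM and ASMI.

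The interval formula depends on the data. The pooled branch is given as: "The t-test will assume Equal variances when the null hypothesis of variance equality cannot be rejected". The alternative branch, in the same sentence of the SAP, is: "Unequal variances when the variance equality hypothesis is rejected". The variance test is not named and its level is not given. No other section overrides the rule.

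The continued-vs-switched comparison of Week 49 SPPB is the primary one (Protocol 9.4.2, SAP 3.4.2). The comparison with continued placebo is secondary. SAP 3.5.3.1 describes it as "the difference between each continued BYM dose arm and the placebo arm continued from the core study at each visit", in the singular, so core-placebo patients appear to form one group.

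On size, Protocol 3.1 says: "It is anticipated that approximately a total 45 patients will be followed under this design". Protocol 5.2 splits each core dose arm 1:1 between continuing and switching, whereas "Patients on BYM338 0 mg (placebo) in core study were randomized 1:1 to receive BYM338 0 mg (placebo) in both arms".

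**The concern.** A non-significant variance test does not show that variances are equal. With very few patients per arm it seldom rejects even when the SDs differ a good deal, so the pooled formula is used by default.

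This does little harm when the arms are of equal size. When they are not, the pooled standard error gives too much weight to the larger arm's variance. The interval is then too short on average if the smaller arm is the more variable, and too long if it is the less variable. Continued drug against continued placebo is the comparison where sizes differ.

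The study does no formal hypothesis testing (Protocol 9.4.2), so a between-arm interval in Population I is read directly as the result, and its stated 95% should be close to true. The rule also lets two endpoints or visits in the same arms be analysed by different formulas through chance variation in the sample variances.

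**Working it through.** **The plan's own precision figure.** Protocol Table 9-2 gives one-arm half-widths. Using 1.96 × SD/√n:
- n = 50: 0.42, 0.55, 0.69, 0.83 for SD 1.5, 2.0, 2.5, 3.0.
- n = 40: 0.46, 0.62, 0.77, 0.93.

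All eight cells reproduce. They concern arms of 40 to 50 patients. No precision figure is given for Population I differences.

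**Inputs.**
- Arm sizes (derived, not stated): about 45 patients over 4 core arms is 45/4 = 11.25 per core arm, if core allocation was equal (an assumption). Splitting 1:1 gives about 5.6 per continued-dose arm. Core placebo stays together at about 11. The base case is 5 vs 11.
- SD ratio, dose arm to placebo arm: Protocol Table 9-1 cites one sarcopenia trial with "1.48 (Baseline) 2.19 (After 6 months treatment") and 1.93 after six months of placebo. The ratio is 2.19/1.93 = 1.13. Ratios of 0.5, 1.5 and 2 are assumptions.
- Variance test: two-sided folded F at 5% (an assumption, since the SAP is silent).

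**Mechanism.** Write the placebo variance as 1 and the dose-arm variance as r². At 5 vs 11:
- true variance of the difference: r²/5 + 1/11
- expected pooled estimate: [(4r² + 10)/14] × (1/5 + 1/11)

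| r | True | Pooled | Square root of pooled/true |
|---|---|---|---|
| 0.5 | 0.141 | 0.229 | 1.27 |
| 1.13 | 0.348 | 0.315 | 0.95 |
| 1.5 | 0.541 | 0.395 | 0.85 |
| 2 | 0.891 | 0.540 | 0.78 |

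With equal arm sizes the two expressions are identical for every r.

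**Coverage of the two-stage rule.** Simulation on normal data, 200,000 to 400,000 datasets per case. Each dataset gets the F test, then the pooled or Welch interval. Repeat runs agree to within about 0.2 percentage point. At 5 vs 11:

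| SD ratio | F test rejects | SAP rule | Welch always |
|---|---|---|---|
| 0.5 | 23% | 97.2% | 95.3% |
| 1 | 5% | 94.9% | 94.9% |
| 1.13 | 7% | 94.0% | 94.8% |
| 1.5 | 18% | 91.8% | 94.4% |
| 2 | 40% | 90.3% | 94.3% |

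**Sensitivity of the SAP rule.**
- 8 vs 11: about 94.6%, 93.9% and 93.5% at ratios 1.13, 1.5 and 2. At 10 vs 11 the shortfall nearly vanishes.
- 4 vs 8 (the base case after the 30% dropout that Protocol section 4 assumes): 94.1%, 91.9% and 89.9%.
- Variance test at 20% instead of 5%, 5 vs 11: 93.0% and 92.6% at ratios 1.5 and 2.
- SPPB rounded to whole points on 0–12, 5 vs 11: 94.1%, 91.8% and 90.3%.
- Primary pairs, 5 vs 5: 95.1%, 94.8% and about 94.5%.

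**Width.** With placebo SD 1.93 and ratio 1.13, the mean half-width at 5 vs 11 is 2.35 SPPB points under the SAP rule and 2.61 under Welch.

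**The case against.** The best defence is that little depends on this. The only SD ratio in the documents is 1.13, and there the loss against Welch is under one point. The larger losses need ratios of 1.5 to 2 that no section supports. Arm sizes are inferred, and so is the pooling of both core-placebo halves, because the figure that defines the comparisons is not available. With 8 vs 11 patients or a 20% test level the shortfall shrinks. The affected comparisons are secondary, in a small legacy subgroup, with no formal testing. A half-width above 2 points, against a clinically relevant change of 1.0 (Protocol 6.3.2), is too imprecise under either method to settle much. The rule is prespecified, and Welch itself falls slightly short at these sizes.

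Most of this stands, and it limits the point to a minor one. It does not justify the rule. The test is not fully specified, it rarely detects the inequality it is meant to detect, and Welch stays nearer 95% at every unequal ratio tried at 5 vs 11.

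A reader might infer that the intervals against placebo are too narrow whenever the dose arm is more variable, or that the primary result is compromised. The documents support neither. Welch is already used in the runs where the test rejects (40% at ratio 2). The true direction of any SD difference in Population I is unknown, and a less variable dose arm makes the intervals too wide. The primary pairs are split 1:1 and stay near 95%.

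**Conclusion.** The point holds as a minor one. The pre-test lets nominal 95% intervals for continued bimagrumab against continued placebo miss 95% coverage in either direction. The miss is about 1 percentage point at the one SD ratio the documents give. It is about 3 to 5 points short at assumed ratios of 1.5 to 2, and about 2 points over at a ratio of 0.5. These sizes rest on equal core allocation, one combined continued-placebo arm, and a two-sided 5% F test, none of which the documents state outright. The primary comparisons keep about 94.5% to 95%. No formal test depends on the affected intervals.

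**What to change.** In SAP 5.8.1, replace the sentence on equal and unequal variances with: *All two-sample 95% confidence intervals use the unequal-variance (Welch-Satterthwaite) method; no preliminary test of variances is done.*

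This is a one-sentence change with no effect on design or data collection, and it removes the unspecified test. The cost is some width if variances are in fact equal: on average about 2% at 6 vs 6, 7% at 5 vs 11 and 13% at 4 vs 11.

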### 5.8.2 ANCOVA

For Population II, ANCOVA model is used to explore the durability of BYM338 on the following endpoints:

- Week 49 on the SPPB
- Week 49 on the 6MWT
- Week 49 on the Gait speed
- Week 49 in log transformed values on LBM and ASMI

[figure not shown]
The endpoint value at extension baseline as a covariate, treatment arm (as assigned in the core study for population II) [REDACTED] will be included as fixed effects. The 95% confidence intervals for the difference between arms receiving BYM338 and Placebo during the core study will be estimated.

[figure not shown]
[REDACTED]

[REDACTED]

[REDACTED]

## **6 Appendix**

### **6.1 Protocol deviations**

Exceptions to the following inclusion/exclusion are considered as major protocol deviations. The list with corresponding actions to remove subjects from certain analysis set will be defined prior to unblinding.

Inclusion/Exclusion Criteria Number	Exclusion Criteria Text
Inclusion	
Inclusion 1	Men and postmenopausal women aged 70 years or older that have participated in, and have completed the full study treatment period per protocol (24 weeks/EOT visit) in the preceding core study (CBYM338E2202);
Inclusion 2	Written informed consent must be obtained before any assessment of the extension study is performed (can be obtained at the EOT visit of the core study).
Exclusion 1	Use of prohibited treatments as per recommendations in Protocol Table 5-1 ;
Exclusion 2	History of severe hypersensitivity reaction in the core study;
Exclusion 3	History of breaking the blind (inadvertently or for emergency reasons) in the core study;
Exclusion 4	History of adverse event(s) in the core study that in the judgement of the investigator, taking into account the subject's overall status, prevent the subject from entering the extension study);
Exclusion 5	Clinically significant abnormal liver function tests that would have resulted in discontinuation of study drug while participating in the core study as per protocol (as outlined in Protocol Appendix 1 ) such as SGOT (AST), SGPT (ALT), alkaline phosphatase, or serum bilirubin (except Gilbert's Disease);
Exclusion 6	Patient has any medical condition or laboratory finding (e.g., an unexplained or clinically significant lab result), which, in the opinion of the investigator taking into consideration the subject's overall status, prevents the subject from continuing participation in the study, may interfere with participation in the study, might confound the results of the study, or pose an additional safety risk to the subject in administering bimagrumab;
Exclusion 7	Concurrent enrollment in a clinical trial involving an investigational drug or off-label use of a drug, or any other type of medical research judged to be scientifically or medically incompatible with this study (not including enrollment in BUM338E2202 core study).

No additional exclusions may be applied by the investigator, in order to ensure that the study population will be representative of all eligible patients, within and across study sites.

